## STUDY SUMMARY

Title	A Prospective Study to Evaluate Quantitative Non-Contrast Perfusion using Arterial Spin Labeled MR Imaging for Assessment of Therapy Response in Metastatic Renal Cell Carcinoma
Short Title	Quantitative MRI for therapy response assessment in metastatic RCC
Protocol Number	STU 032018-078
Phase	N/A
Methodology	Prospective study to evaluate quantitative MRI metrics for the assessment of treatment response
Study Duration	48 months
Study Center(s)	Single-center
Objectives	To prospectively determine whether ASL-measured perfusion can identify treatment response earlier than the currently used RECIST criteria.
Number of Subjects	90 (40 subjects with RCC and 50 healthy volunteers)
Diagnosis and Main Inclusion Criteria	Diagnosis: Locally advanced or metastatic renal cell carcinoma Main Inclusion Criteria: Patients with histologically proven clear cell RCC, scheduled to undergo anti-angiogenic treatment or immunotherapy (IO) who are 18 years of age and older and have no contraindication to MRI.
Study Product(s), Dose, Route, Regimen	N/A
Duration of administration	N/A
Reference therapy	N/A
Statistical Methodology	Primary end points for this study will include the absolute days of time to disease progression, progression free survival (PFS) and overall survival (OS) as well as disease status (progression versus not) at 7 months post treatment initiation. Progression will be determined according to the clinical RECIST criteria. One-sample correlation test will be used to determine the correlation between change in ASL measured tumor perfusion during and immediately after treatment and time to progression, and the correlation between change in ASL measured tumor perfusion and the corresponding tumor size change. The correlations will be measured and compared using Pearson's correlation coefficient along with 95% confidence interval. PFS and OS will be correlated with baseline perfusion and post-treatment changes at T1, T2 and T3 compared to baseline using univariable and multivariable Cox regression models. Univariable and multivariable logistic regression models will be used to predict responders from non-responders (progression versus not at 7 months) with ASL measurements at baseline and at earlier time points (T1 and T2) alone, and in combination with other MR imaging metrics.

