### **2.0 STUDY OBJECTIVES**

#### **2.1 Primary Objectives**

- 2.1.1 To determine whether ASL-measured perfusion can identify treatment response (time to progression) earlier than the currently used RECIST criteria in patients undergoing anti-angiogenic treatment.

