#### **2.3 Exploratory Objectives**

- 2.3.1 To determine whether ASL-measured perfusion can identify treatment response (time to progression) earlier than the currently used RECIST criteria in patients undergoing IO.

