**10.0 STATISTICAL CONSIDERATIONS**

**10.1 Study Design/Study Endpoints**

This is a prospective, single-centered study, designed to address the following primary objective:

1. To determine whether ASL-measured perfusion can identify treatment response (time to progression) earlier than the currently used RECIST criteria (tumor size).  
*Hypothesis: Greater reduction in ASL measured tumor perfusion during and immediately after treatment is a marker of tumor responsiveness prior to size changes.*

Primary end points for this study will include the absolute days of time to disease progression, PFS and OS as well as disease status (progression versus not) at 7 months post treatment initiation. Progression will be determined based on clinically accepted RECIST criteria (20).

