**10.2 Sample Size and Accrual**

The sample size is calculated based on the primary objective. A significant correlation of 0.75 was observed between one month ASL perfusion change and time to progression in our RCC patients, whereas the corresponding tumor size change was not correlated with time to progression (19). We expect approximately 50% of RCC patients to progress within 7 months of imaging protocol. Beyond this time point, patients will be followed according to their clinical scans for the next 3 years or until death. Using such information, we target 40 subjects for this study and anticipate approximately 20 subjects to progress within the 7 months period. This sample size would provide more than 95% power to detect a correlation of 0.75 between earlier perfusion changes (at T2 and T6) and time to progression, using two-sided correlation test at a significance level of 0.05.

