**10.3 Data Analyses Plans**

The perfusion difference images and the absolute quantified images will be converted to DICOM and transferred to a DICOM database (e.g. iPACS, OsiriX). A semi-automated segmentation algorithm and region of interest (ROI) based measures will be performed to extract perfusion measures. Percentage changes in perfusion within each ROI will be calculated at each follow-up MRI compared to the baseline image. The semi-automated tumor ROIs will be compared to expert segmentation by [name] in all cases, who will also supervise the trainee (to be recruited) in the analysis. Additionally, morphological changes will also be calculated according to RECIST and 10% reduction in the sum of the largest diameters (20).

Among patients with disease progression, one-sample correlation test will be used to determine the correlation between change in ASL measured tumor perfusion during and immediately after treatment and time to progression, and the correlation between change in ASL measured tumor perfusion during and immediately after treatment and the corresponding tumor size change. The correlations will be measured and compared using Pearson's correlation coefficient along with 95% confidence interval. PFS and OS will be correlated with baseline perfusion and post-treatment changes at T1 and T2

compared to baseline using univariable and multivariable Cox regression models. We used PFS at 7 months as a cutoff point to divide patients into “responders” versus “non-responders” in this study. Univariable and multivariable logistic regression models will be used to predict responders from non-responders with ASL measurements at baseline and at earlier time points (T1 and T2) alone, and in combination with other MR imaging metrics. The statistical analysis will also be performed separately for male and female subjects to evaluate sex as a biological variable.

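### The primary objective sets ASL perfusion against RECIST tumor size, but no listed analysis relates size change to time to progression

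*Combined protocol and SAP*

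**What the plan says.** Section 10.1 gives the primary objective as "To determine whether ASL-measured perfusion can identify treatment response (time to progression) earlier than the currently used RECIST criteria (tumor size", with the hypothesis that a fall in perfusion marks responsiveness before size changes. The outcome is itself size-based: "Progression will be determined based on clinically accepted RECIST criteria (20".

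Section 10.2 starts from a two-part contrast in previous data. One-month perfusion change correlated 0.75 with TTP, "whereas the corresponding tumor size change was not correlated with time to progression (19". On sample size: "we target 40 subjects for this study and anticipate approximately 20 subjects to progress within the 7 months period". Power is stated as more than 95% to detect a correlation of 0.75 between early perfusion change and TTP, two-sided, at 0.05.

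Section 10.3, among patients with progression, names the perfusion-TTP correlation "and the correlation between change in ASL measured tumor perfusion during and immediately after treatment and the corresponding tumor size change". The Study Summary names the same pair: "and the correlation between change in ASL measured tumor perfusion and the corresponding tumor size change". Section 10.3 adds that the correlations will be measured and compared by Pearson's coefficient with 95% confidence intervals, and that size changes will be calculated by RECIST and by a 10% reduction criterion.

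**The concern.** The objective has a comparator, tumor size, and the justification in 10.2 has two halves: perfusion relates to TTP and size does not. The analysis plan repeats only the first half. Size change is derived but never used as a predictor of outcome.

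If the plan is followed exactly, a positive result shows that early perfusion change is associated with later RECIST progression, and whether perfusion and size changes move together. It does not show whether size change relates to TTP less strongly than perfusion does. Any such comparison would have to be devised after the data are seen.

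**Working it through.** **Inputs.** From section 10.2: r(perfusion,TTP) = 0.75, 40 RCC subjects, about 20 progressing within 7 months, two-sided 0.05, then 3 years of follow-up. The documents give no value for r(size,TTP), only that it was not correlated, and none for r(perfusion,size). I assume 0 or 0.3 for the first and 0 to 0.5 for the second.

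**1. Which relations are analysed.**

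| Relation | Where specified |
|---|---|
| Perfusion change and TTP | Study Summary, 10.3 |
| Perfusion change and size change | Study Summary, 10.3 |
| Baseline perfusion and post-treatment changes (perfusion changes, per 2.2.2) with PFS and OS | Study Summary, 10.3 (Cox) |
| ASL alone, or with other MR metrics (2.2.3 names ADC and CEST), with 7-month status | Study Summary, 10.3 (logistic) |
| Size change and any outcome | Nowhere |

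**2. The plan's own power.** Fisher z: Φ(atanh(0.75)·√(20−3) − 1.96) = Φ(0.973 × 4.123 − 1.96) = Φ(2.05) = 98.0%. The stated figure holds, for perfusion-TTP against zero.

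**3. Can the two planned correlations supply the third?** Given a = r(perfusion,TTP) and s = r(perfusion,size), r(size,TTP) can lie anywhere in a·s ± √[(1−a²)(1−s²)].
- a = 0.75, s = 0.3: 0.225 ± √(0.4375 × 0.91) = −0.41 to 0.86.
- a = 0.75, s = 0.5: 0.375 ± √(0.4375 × 0.75) = −0.20 to 0.95.

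So they cannot.

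**4. What a non-significant size correlation would show.** At n = 20 a correlation must exceed about 0.44 in absolute value to be significant. An observed size-TTP correlation of 0.3 would therefore be non-significant, with 95% CI tanh(atanh(0.3) ± 1.96/√17) = −0.16 to 0.66. Against 0.75, the difference is 0.45. Zou's interval, which combines the two Fisher-z intervals and allows for their dependence, is −0.03 to 0.95 if s = 0 and 0.04 to 0.91 if s = 0.3. Whether a difference is shown depends on a quantity that must be estimated directly.

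If size-TTP were exactly 0, Zou's intervals for the difference of 0.75 would be:

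| n | s = 0 | s = 0.5 |
|---|---|---|
| 20 | 0.22 to 1.22 | 0.36 to 1.14 |
| 15 | 0.12 to 1.29 | 0.29 to 1.20 |
| 10 | −0.07 to 1.41 | 0.17 to 1.31 |

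**5. Power for the difference.** Williams test for two dependent correlations sharing TTP, n − 3 df, two-sided 0.05, r(perfusion,TTP) = 0.75, simulated with 40,000 trivariate normal samples. Ranges run over s = 0 to 0.5.

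| n | r(size,TTP) = 0 | r(size,TTP) = 0.3 |
|---|---|---|
| 39 | about 99% or more | 77% to about 97% |
| 20 | 83% to over 99% | 45% to 74% |
| 15 | 68% to 98% | 33% to 59% |
| 10 | 45% to 88% | 19% to 37% |

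The n = 39 row covers another reading of 10.3, which does not limit progression to 7 months. With a constant hazard and a median of 7 months, 1 − 0.5^(36/7) = 97% progress by 36 months, and 40 × 0.97 is about 39. The rows for 15 and 10 assume that 75% or 50% of the 20 are usable.

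**The case against.** **The plan does compare correlations.** It does, but the two it names are perfusion-TTP and perfusion-size. Their difference says nothing about size and TTP. What stands is that the perfusion-size correlation bears on redundancy: a value near zero would suggest that the two measures carry different information. It does not show which of them relates to TTP.

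**Size may count among the other MR metrics.** The wording in 2.2.3 is not exhaustive, but no section names size, and those models serve a secondary objective.

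**Earlier is a question of timing.** Perfusion is read at days 7 and 14, clinical imaging comes every 2 to 3 months, and section 5.4 expects no size change sooner. An early perfusion change that correlates with later RECIST progression partly meets the objective. This stands. It also means that a comparison of correlations measures relative strength, not earliness, and that size at T1 or T2 may be a weak comparator.

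**Two stronger readings are tempting.** A reader might infer that the stated power is wrong; it reproduces. A reader might also infer that repeating the pattern in 10.2 (0.75 for perfusion, 0 for size) could not establish a difference. The intervals in the working do not support that: all exclude zero except at n = 10 with s = 0.

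**Conclusion.** The gap is real and can be read from the text alone: the comparator in the primary objective is measured but never related to outcome. The conclusion is limited to that. The plan can still show that early perfusion change is associated with later progression, and nothing here says that the comparison would fail once made.

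The stated 98% does not carry over to the comparison. At about 20 progressors, power for the difference is good if size is unrelated to TTP (83% to over 99%) and modest if that correlation is 0.3 (45% to 74%). At 39 progressors both cases are better. These figures rest on assumed values for r(size,TTP) and r(perfusion,size), on normality, and on 0.75 holding at the early visits although it was observed at one month.

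Fewer usable patients would lower them. The primary objective concerns response "earlier than the currently used RECIST criteria in patients undergoing anti-angiogenic treatment", with immunotherapy exploratory ("earlier than the currently used RECIST criteria in patients undergoing IO"), while the 20 progressors are drawn from all 40 subjects. That mismatch, and the missing date for T3 in RCC subjects, are separate matters that add no weight to this point.

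**What to change.** In the Study Summary and section 10.3:

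1. Add the correlation of RECIST size change with TTP, with 95% CI, in the same patients and at the same visits as the perfusion change. State that size is read on the T1 and T2 images where these cover the target lesions.
2. Code both changes as reductions. Give a CI (for example Zou) and a test (for example Williams) for the difference between the two dependent correlations. Label it as relative strength of association at the same early visit, not as a direct test of earliness.
3. Keep the perfusion-size correlation as descriptive.
4. State as a limitation that TTP is itself defined by RECIST.
5. Treat a T3 comparison as optional and partly circular. Under a constant hazard with a 7-month median, 36% to 51% of seven-month progressors would have progressed by a T3 at 2 to 3 months: (1 − 0.5^(2/7))/0.5 and (1 − 0.5^(3/7))/0.5.

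In sections 10.2 and 10.3, state whether the correlation set is 7-month progressors or all progressors during follow-up, and give power for the difference as a range.

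**Cost.** A little more analysis and a less favourable power figure for the comparison. Section 10.3 already calculates size change. However, the events table marks tumor measurements only at pre-study, T1 and T2 lesion coverage is not stated, and the Study Schema makes attendance at both visits optional. The number of patients with usable size readings should therefore be reported.

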#### 5.4 Time and Events Table

##### RCC Subjects

	Pre-study	Week 0 (T0) before initiation of anti-angiogenic therapy	Day 7±2 (T1)	Day 14±2 (T2)	T3	T4	T5	Follow-up (As indicated by clinical protocol)
Assessment	X							
Informed Consent	X							
History and PE	X							
Tumor Measurements	X							
MRI*		X	X	X	X	X	X	X

\*Clinically, metastatic RCC patients are imaged every 2-3 months after the initiation of anti-angiogenic therapy, since morphological (i.e. size) changes are not anticipated earlier. However, our preliminary experience has shown functional changes including perfusion as early as 2-weeks after the initiation of the treatment (19). T0, T1, and T2 sessions will be performed for this proposal, while T3, T4, and T5 will be performed along with the clinical imaging sessions. The research MR imaging may take approximately an additional 15 minutes per each imaging session, when done in conjunction with the clinical imaging. The T0, T1, and T2 research MR imaging sessions will be performed additionally for the purpose of this study, with each taking approximately one hour.

The ASL portion of the study does not require contrast. Clinically, the subjects will also receive gadolinium based contrast injection for the MRI study to measure the blood flow to the tumors. This is done at the clinical imaging time points of T3, T4, and T5. Similar to this, the contrast agent will also be administered during the research portion of the study at T0, T1 and T2 time points, to compare the blood flow measured with ASL-MRI.

MRI including ASL will be performed before, during and after the treatment, in a total of 6 MRI sessions until 7 months after the first session, or when progression is clinically indicated. Thereafter, patients will be followed through standard clinical examinations for the next 3 years or until demise, whichever occurs first.

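### The planned perfusion–size correlation names no visit and, read as same-time, cannot show that perfusion change precedes size change; no planned analysis compares the two as early markers

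*Combined protocol and SAP*

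**What the plan says.** The hypothesis in section 10.1 is one of timing: a greater fall in perfusion "is a marker of tumor responsiveness prior to size changes". The primary objective (2.1.1) concerns patients on anti-angiogenic treatment; the same question under immunotherapy (IO) is exploratory (2.3.1).

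Section 10.3 plans two Pearson correlations with 95% confidence intervals: "Among patients with disease progression, one-sample correlation test will be used" for perfusion change against time to progression, and for "the correlation between change in ASL measured tumor perfusion during and immediately after treatment and the corresponding tumor size change". The Study Summary repeats the pair. Neither place gives a visit or a lag for the second correlation. Section 10.2 uses the word *corresponding* for the size change that goes with a one-month perfusion change, so same-interval is the natural reading, though it is not stated outright.

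The footnote to the RCC table in section 5.4 explains that clinical scans are taken every 2–3 months "since morphological (i.e. size) changes are not anticipated earlier", while perfusion may change by 2 weeks. T1 is day 7±2 and T2 is day 14±2; T3 to T5 coincide with clinical scans.

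On size, section 10.2 says "we target 40 subjects for this study" and that the investigators "anticipate approximately 20 subjects to progress within the 7 months period". It claims: "This sample size would provide more than 95% power to detect a correlation of 0.75" between perfusion change and time to progression, with a "two-sided correlation test at a significance level of 0.05". It places those perfusion changes at T2 and T6, but the schedule ends at T5.

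**The concern.** To support the hypothesis, an analysis must show either that early perfusion change is followed by later size change, or that early perfusion change tells more about outcome than early size change does. Correlating two changes measured over the same interval does neither.

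At T1 and T2 the protocol's own premise is that size has barely moved. The size change is then largely measurement error, and a low correlation is what one would see both when perfusion foretells later shrinkage or growth and when it has nothing to do with size. At T3 to T5 size change is expected, but a high same-time correlation shows only that the two move together.

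With the visit left open, the choice could also be made after the data are seen. At stake is whether the study can report a result on timing at all, or only that perfusion change is associated with outcome.

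**Working it through.** **1. The plan's own figure.** Inputs from section 10.2: n = 20 progressors, r = 0.75, two-sided alpha 0.05. By Fisher's z, power = Φ(atanh(r)·√(n−3) − 1.96) = Φ(0.973 × 4.123 − 1.96) = Φ(2.05) = 98.0%. Simulation of the t-test for Pearson's r gives 98.4%. The claim of more than 95% reproduces (95% is reached from n = 17). It covers perfusion against time to progression only; no power is stated for perfusion against size.

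**2. What each planned analysis can say about timing.**

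| Analysis in 10.3 | Perfusion against a later outcome? | Early size as comparator? |
|---|---|---|
| Perfusion change vs time to progression | Yes, if the perfusion visit is early | No |
| Perfusion change vs corresponding size change | No, as naturally read | Not as a predictor of outcome |
| Cox models of PFS and OS on baseline perfusion and T1/T2 changes | Yes | No |
| Logistic models of 7-month status on baseline and T1/T2 | Yes | None named; 2.2.3 gives diffusion and CEST as examples of the other MR metrics |

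Section 10.3 says the two correlations will be compared. Setting r(perfusion, time to progression) against r(perfusion, size) does not compare perfusion and size as predictors. The comparison that would do so is the one section 10.2 cites from earlier data: one-month perfusion change correlated 0.75 with time to progression, and size change did not correlate with it. Section 10.3 does not carry it forward.

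**3. How low the same-time correlation would be at T1/T2.** Expected observed r = r_true × √(rel_perfusion × rel_size), where each reliability = SD_true² / (SD_true² + SD_error²).

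- From the documents: the within-subject coefficient of variation of perfusion is 7% (section 6.1), so the error SD of a change is about 7 × √2 = 9.9 percentage points.
- Assumed, not in the documents: true perfusion–size r of 0.5–0.75; true SD of perfusion change 15–40 points; error SD of early size change 5–10 points; true between-patient SD of early size change 0–10 points.

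Worked example: perfusion SD 25, size SD 2, size error SD 5, r_true 0.75. Then rel_perfusion = 625/(625 + 98) = 0.86, rel_size = 4/29 = 0.14, and r = 0.75 × √(0.86 × 0.14) = 0.26, with power 19% at n = 20.

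| True SD of early size change (points) | Expected observed r | Power, n = 20 |
|---|---|---|
| 0 | 0 | 5% (false-positive rate) |
| 2 | 0.08–0.27 | 6–21% |
| 5 | 0.19–0.51 | 12–65% |
| 10 | 0.30–0.65 | 24–89% |

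**4. Precision.** At n = 20 an observed r of 0 has a 95% interval of ±tanh(1.96/√17) = ±0.44, and |r| must exceed 0.44 to be significant.

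**5. Can the statistic tell lead from no lead?** Simulated with 20 patients and early size change that is pure noise:

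| Truth | Same-time r: median, rejections | Early perfusion vs later size: median, rejections |
|---|---|---|
| Perfusion leads (lagged r = 0.75) | 0.00, 5% | 0.76, 98% |
| Perfusion does not lead | 0.00, 5% | 0.00, 5% |

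In this limiting case the same-time statistic behaves identically under both truths; the lagged one separates them.

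**6. The missing comparator.** Williams' test of r(perfusion, time to progression) = 0.75 against r(early size, time to progression), n = 20, with perfusion–size r assumed between 0 and 0.4: power 83–98% if the size correlation is 0, 59–82% if 0.2, 45–66% if 0.3, and 20–28% if 0.5.

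**The case against.** The strongest reply is that this is one correlation among several and does not carry the timing claim alone. Perfusion change is also correlated with time to progression, and T1/T2 changes enter Cox models for PFS and logistic models for 7-month progression. Progression is defined by RECIST, including a 20% rise in the sum of longest diameters (6.1.3.1), so early perfusion is already tested against a later, largely size-based outcome. This stands, and a reader who inferred that the plan has no forward-looking analysis would be wrong. These analyses can show that early perfusion predicts outcome; they cannot show that it does so sooner or better than size measured at the same visit.

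The second reply is that T1/T2 is an inference. Section 10.3 computes perfusion change at every follow-up MRI, and its description of the timing could take in T3 to T5, where size change is expected. This also stands, which is why the point about a low value is conditional on T1/T2.

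A reader might go further and infer that a near-zero result is built into the plan. The documents do not support that. An absence of expected change on average does not force a zero correlation: the value depends on between-patient spread and measurement error, neither of which is given, and the assumptions above allow up to about 0.65. Nor does any section say that a low value would be taken as support for the hypothesis.

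**Conclusion.** The point holds in limited form. The perfusion–size correlation lacks a stated visit and lag. If it is meant for T1/T2, a low value is likely whether or not perfusion leads size. At any visit, a same-time correlation carries no information on lead. The rest of the plan relates early perfusion to later progression but has no early-size comparator, so earlier than RECIST is not tested directly.

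The first and last of these conclusions rest on the text alone; the others also take *corresponding* to mean same-interval. The sizes (expected r from 0 to about 0.65 and the accompanying power) rest on assumed SDs and correlations and are illustrative. The ±0.44 interval needs only n = 20, and that n is itself generous: the anticipated 20 progressors are drawn from all 40 RCC patients, and the documents do not give the split between anti-angiogenic treatment and IO. The stated power for perfusion against time to progression is not in question here.

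**What to change.** In section 10.3 and the Study Summary:

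1. Add the correlation of T2 perfusion change with percentage change in the sum of longest diameters from T0 to T3, in anti-angiogenic-treated RCC patients with both measurements. Analyse IO patients separately as exploratory, in line with 2.1.1 and 2.3.1. Record the actual T3 date, since T3 follows clinical imaging and has no fixed day. State that this analysis is not confined to progressors.
2. Add the correlation of early (T1/T2) size change with time to progression, in the same patients as the perfusion correlation, and compare the two with a named test for dependent correlations such as Williams' test.
3. Name the visits for the same-time perfusion–size correlation. Keep it at T1/T2 as descriptive only, and state that a low value is not evidence of lead.
4. Reconcile the reference to T2 and T6 in section 10.2 with the T0–T5 schedule.

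Cost: analysis wording only. T0 to T3 imaging is already scheduled, and perfusion and size changes are already to be calculated. The downside is loss of patients: the Study Schema makes attendance at both early visits optional, and some patients will leave or die before T3. Those missing T2 or T3 do not contribute and should be counted and reported. Precision will be limited at about 20 patients, and any power quoted for the added analyses should be labelled as resting on assumed values.

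### Section 10.3 compares two dependent correlations with no test or interval for their difference and no sign convention, and the pair it names is not the one the primary objective needs

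*Combined protocol and SAP*

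**What the plan says.** Section 10.3 restricts the correlation analysis to patients who progress: "Among patients with disease progression, one-sample correlation test will be used". It is applied to perfusion change with time to progression, and also to "the correlation between change in ASL measured tumor perfusion during and immediately after treatment and the corresponding tumor size change". The comparison is then described in one sentence: "The correlations will be measured and compared using Pearson's correlation coefficient along with 95% confidence interval". The Statistical Methodology row of the Study Summary carries the same sentence.

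Section 10.3 computes perfusion as a percentage change from baseline at each follow-up MRI. The hypothesis in 10.1 is directional: "Greater reduction in ASL measured tumor perfusion during and immediately after treatment is a marker of tumor responsiveness".

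Section 10.2 supplies the planning values. For perfusion: "A significant correlation of 0.75 was observed between one month ASL perfusion change and time to progression in our RCC patients". For size: "the corresponding tumor size change was not correlated with time to progression", with no number given. On numbers of patients: "we target 40 subjects for this study and anticipate approximately 20 subjects to progress within the 7 months period". The power claim is "more than 95% power to detect a correlation of 0.75 between earlier perfusion changes" and time to progression, at a two-sided 0.05 level.

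**The concern.** A Pearson coefficient with its 95% confidence interval describes one correlation. Comparing two needs an interval or test for their difference. When both come from the same patients and share a variable, that difference also depends on the third correlation, here size change with time to progression. Section 10.3 gives no such method and no decision rule.

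The signs are also left open. With percentage change from baseline, a larger fall is a more negative number, so the 10.1 hypothesis implies a negative correlation with time to progression. If perfusion and size fall together, their correlation is positive. The positive 0.75 in 10.2 agrees with the hypothesis only if change is coded as a reduction, and 10.3 does not say that it is.

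The primary objective is comparative (perfusion against RECIST size), and this sentence is the only place in 10.3 where correlations are explicitly compared. An analyst who follows it literally could miss a real difference under one coding, or report one that is only a matter of sign under the other.

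**Working it through.** **Notation.** P = perfusion change, T = time to progression, S = size change; r1 = corr(P,T), r2 = corr(P,S), r3 = corr(T,S).

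**Inputs.** From 10.2: r1 = 0.75, about 20 progressors, two-sided 0.05, and r3 taken as 0 because size change is described as uncorrelated with time to progression. The documents give no r2, so it is assumed and varied.

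**1. The plan's own figure.** Power for one correlation against zero by Fisher's z: Φ(atanh(0.75)·√(20−3) − 1.96) = Φ(0.973 × 4.123 − 1.96) = Φ(2.05) = 98%. The claim of more than 95% reproduces. It concerns r1 alone.

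**2. One interval per coefficient.** The 95% interval is tanh(atanh(r) ± 1.96/√17), with half-width 0.475 on the z scale.
- r = 0.75: 0.46 to 0.90
- r = 0.20: −0.27 to 0.59, which overlaps the first
- For no overlap with 0.75, the second coefficient must be below tanh(0.973 − 0.951) = 0.02.

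**3. A dependent-correlation test on the same values.** Williams' statistic on n − 3 degrees of freedom is

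t = (r1 − r2)·√{(n−1)(1+r3) / [2·((n−1)/(n−3))·D + ((r1+r2)/2)²·(1−r3)³]}, with D = 1 − r1² − r2² − r3² + 2·r1·r2·r3.

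With observed values 0.75, 0.20 and 0 at n = 20: D = 1 − 0.5625 − 0.04 = 0.3975. The denominator is 2 × (19/17) × 0.3975 + 0.475² = 0.889 + 0.226 = 1.114. So t = 0.55 × √(19/1.114) = 2.27, against a critical value of 2.11 (p = 0.036). The same data give overlapping intervals and a significant difference.

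**4. Chance of showing a real difference.** Trivariate-normal simulation, 50,000 samples per scenario, signs aligned, r1 = 0.75, r3 = 0:

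| n | r2 | Intervals do not overlap | Williams' test |
|---|---|---|---|
| 20 | 0 | 55% | 83% |
| 20 | 0.2 | 32% | 59% |
| 20 | 0.3 | 22% | 45% |
| 30 | 0 | 81% | 96% |
| 30 | 0.3 | 38% | 65% |
| 40 | 0 | 93% | 99% |
| 40 | 0.3 | 54% | 78% |

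With equal aligned correlations at n = 20, non-overlap gives a false difference in 0.1% to 0.9% of trials and Williams' test in 4.5% to 4.8%. The non-overlap rule is therefore far stricter than a 5% test.

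**5. Signs.** Take equally strong correlations of −0.5 and +0.5 at n = 20. Their intervals, −0.77 to −0.07 and 0.07 to 0.77, do not overlap. In simulation, non-overlap occurs in 68% to 71% of trials and Williams' test is significant in 86% to 96% (r3 from −0.3 to 0). After alignment, Williams' error returns to about 5%. Alignment cures this fault; the choice of test does not.

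**6. Which pair is compared.** The objective asks whether perfusion relates to time to progression better than size does, so it needs corr(P,T) against corr(S,T). Section 10.3 sets corr(P,T) against corr(P,S). These can be equal while perfusion is still far better: 0.75, 0.75 and corr(S,T) = 0.13 is a valid correlation matrix (D = 1 − 0.5625 − 0.5625 − 0.0169 + 0.1463 = 0.004, positive). For the pair the objective needs, at 0.75 against 0 and with an assumed perfusion-size correlation of 0, Williams' test has about 83% power at n = 20.

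**The case against.** The strongest reply is that the plan never commits to the rule being criticised. It does not say that the intervals are separate or that overlap decides, and an interval for the difference would fit its wording. That stands: the sentence is under-specified, and the overlap figures apply only if it is carried out as one interval per coefficient.

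A reader might infer that the planned comparison misses most real differences. The documents do not support that in general. At r2 = 0 non-overlap detects about 55%; the statement is true only with aligned signs, about 20 progressors and r2 of roughly 0.2 or more, and r2 is not given. At r2 = 0.3 Williams' test also misses more than half. Larger gains can be produced by letting size change correlate with time to progression, but 10.2 describes it as uncorrelated.

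A reader might also combine missed and false differences into one result. They arise under different codings: missed differences when signs are aligned, false ones when they are not. The wording of 10.1 and the positive 0.75 in 10.2 suggest reduction coding was intended, which makes the sign fault avoidable, but 10.3 does not fix it.

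The figure of 20 is the 7-month expectation; 10.3 sets no such limit, and follow-up continues for 3 years. More progressors help. At r2 = 0 the gap falls from 28 points at n = 20 to 6 at n = 40. At r2 = 0.3 it stays near 24 points, although non-overlap itself rises to 54%.

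Finally, 10.2 might be read as promising more than 95% power for the comparison. It does not: it refers to a single correlation, and that figure is right.

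**Conclusion.** The point holds as a fault in the method named for the comparison. Two overlapping, dependent correlations are to be compared by a tool that describes one at a time, with no sign convention. If that means one interval per coefficient with aligned signs, the chance of showing a real difference at n = 20 is lower than with Williams' test by about 28, 27 and 23 percentage points at r2 = 0, 0.2 and 0.3. If raw percentage changes are used instead, equal strengths of 0.5 would appear different in about 70% of trials. These figures rest on trivariate normality, r1 = 0.75, assumed values of r2, and size change uncorrelated with time to progression (the sign scenario also tried −0.3).

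The pair compared also does not answer the primary objective, so improving the test for that pair alone would not be enough. The documents do not support reading this as an error in the sample size. Nor do they name a comparison of T1 with T2 correlations, so the point does not extend there.

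**What to change.** In 10.3, and in the matching sentence of the Study Summary, replace the comparison sentence with text to this effect:

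- Perfusion and size changes are both coded as reductions: (baseline minus follow-up) divided by baseline.
- Correlations from the same patients are compared by their difference with a 95% confidence interval that allows for dependence, or by the Williams/Steiger test for overlapping correlations. Zou's interval is one option; it held a 5.0% to 5.5% error rate at n = 20 in the same type of simulation.
- The comparison addressing the primary objective is perfusion change with time to progression against size change with time to progression. The comparison already in 10.3 may be kept as supportive.

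The cost is a few sentences and slightly more analysis work. Size change and time to progression are already collected, so no new data are needed. The 10.2 power statement needs no change.
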